6. RATIONALE AND BACKGROUND

6.1. Background

Cabotegravir (CAB), a human immunodeficiency virus type-1 (HIV-1) integrase strand transfer inhibitor (INSTI), in combination with Rilpivirine (RPV), an HIV-1 non-nucleoside reverse transcriptase inhibitor (NNRTI), is indicated as a complete regimen for the treatment of Human Immunodeficiency Virus type 1 (HIV-1) infection in adults who are virologically suppressed (HIV-1 RNA <50 copies/mL) on a stable antiretroviral (ART) regimen without present or past evidence of viral resistance to, and no prior virological failure with agents of the NNRTI and INSTI class. Prior to the initiation of CAB long acting (LA) injection, CAB tablets together with RPV tablets should be taken for approximately one month (at least 28 days) to assess tolerability to CAB and RPV.

Treatment with CAB+RPV LA should be prescribed by a physician experienced in the management of HIV infection. Each injection should be administered by a healthcare provider (HCP). Prior to starting the regimen, the HCP should carefully select individuals who agree to the required injection schedule and counsel individuals about the importance of adherence to scheduled dosing visits to help maintain virologic suppression and reduce the risk of viral rebound and potential development of resistance associated with missed doses. Following discontinuation of CAB+RPV LA injection, it is essential to adopt an alternative, fully suppressive ARV regimen per the summary of product characterization (SmPC).

The Marketing Authorization Holders (MAH) propose a five-year Drug Utilization Study (DUS) to be conducted in a real-world clinical setting. This prospective observational cohort study will aim to better understand the individual population receiving CAB and/or RPV LA containing regimens in routine clinical practice, usage patterns, adherence, post marketing clinical effectiveness of these regimens and monitor for resistance among virologic failures for whom data on resistance testing are available.

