 - d. Assessment of VL for PLWH on other regimen combinations (b-f in objective 1) at 6, 12 and 24 months after initiation of the regimen
- 4. Monitor for resistance and next treatment response among individuals who discontinued CAB+RPV LA, where VL data are available and resistance testing has been done as part of routine clinical practise
 - Describe the ARV regimen individuals are switched to after discontinuation of CAB+RPV LA containing regimens
 - Monitor for resistance (where this has been done as part of routine clinical practise) during the 48 months following the switch
 - Describe virologic outcomes at 12, 24, 36 and 48 months after discontinuation of CAB+RPV LA containing regimens
- 5. Evaluate the effectiveness of routine risk minimisation measures for regimen adherence, discontinuation due to incorrect route of administration and off-label use of CAB+RPV LA regimen
 - Assess off-label use as described in objective 1
 - Estimate proportion of treatment naive or individuals not suppressed initiating regimen
 - Assess non-adherence to the dosing schedule as described in objective 2
 - Assess the frequency of discontinuation due to incorrect route of administration

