2. Clinical effectiveness: Primary analysis for clinical effectiveness will include only those initiating the regimen per label i.e. initiating CAB+RPV LA with VL<50 copies/mL at regimen initiation. The following VL measures will be used for effectiveness assessment:

- 1. Proportion of individuals, virologically suppressed/undetectable (<50 copies/mL) at 6, 12 and 24 months following initiation of CAB+RPV LA regimen
- 2. Proportion of individuals with VL <200 copies/mL at 6, 12 and 24 months following initiation of CAB+RPV LA regimen
- 3. Proportion of individuals with confirmed virologic failure (CVF) during the first 6 months, and at 6, 12 and 24 months following initiation of CAB+RPV LA regimen defined as:
 - Two consecutive HIV RNA VL levels ≥200 copies/mL or
 - One HIV RNA VL level ≥200 copies/mL and regimen discontinuation within 4 months of VL ≥200 copies/mL

3. Resistance Testing:

Since this is a non-interventional study aiming to capture individual care in real world setting, the study will not mandate resistance testing following discontinuation of CAB+RPV LA regimen. Health care providers following the local treatment guidelines decide what laboratory and resistance tests are to be conducted. Data thus generated, including available HIV-1 subtypes, will be captured and analyzed by the study team.

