8.3.3. Confounders and effect modifiers

The study will examine the effect of potential confounders and effect modifiers as shown in Table 2 above on the risk for outcomes of interest.

Demographic variables

- Age
- Sex
- Route of HIV Infection
- Number of years since HIV diagnosis
- Ethnic origin
- Geographic region
- Date of ART initiation

Date CAB and/or RPV LA started

Virologic variables at regimen initiation

- HIV VL at initiation of CAB LA and/or RPV LA containing regimens (and in the 12 months prior to regimen start)
 - o Continuous (copies/mL)
 - o Categorical:
 - <50 copies/mL (or < LOD in clinics where LOD > 50 copies/mL)
 - $\ge 50 \text{ to } < 200 \text{ copies/mL}$
 - $\ge 200 \text{ to } < 10,000 \text{ copies/mL}$
 - \geq 10,000 to <100,000 copies/mL
 - \geq 100,000 copies/mL

Immunologic variables at regimen initiation

- CD4 cell count at initiation of CAB LA and/or RPV LA containing regimens (and in the 12 months prior to regimen start)
 - Continuous (cells/μL)
 - o Categorical:
 - CD4 \geq 500 cells/ μ L
 - CD4 count \geq 350 to <500 cells/ μ L
 - CD4 count <350 cells/µL
- CD4 nadir prior to initiation of CAB LA and/or RPV LA based ARV regimens

Clinical variables at regimen initiation

- HIV Subtype where available
- History of previous use of integrase inhibitor-based or NNRTI-based regimen
- History of previous antiretroviral exposure
- History of previous virologic failure
- History of previous HIV drug resistance and any historical HIV-1 subtype information, where available
- Body Mass Index (BMI), height, weight
- History of AIDS-defining Events (ADE)
- Concurrent medications (Etravirine, Rifampicin, Rifapentine, Rifabutin, Ribavirin, Ketoconazole, Fluconazole, Itraconazole, Clarithromycin, Erythromycin and other medications where data are available)
- Comorbidities (all defined to be consistent with published EuroSIDA analyses)
 - o HCV co-infection [3]
 - o HBV co-infection [4]
 - o End Stage Liver Disease (ESLD) (hepatocellular carcinoma, ascites, hepatorenal syndrome, grade III/IV hepatic

- encephalopathy, unspecified liver decompensation, oesophageal variceal bleeding, liver transplantation) [3]
- Cardiovascular Disease (CVD) (myocardial infarction, stroke, invasive coronary procedure) [3]

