Descriptive analyses will compare those with and without virologic failure to assess any differences in baseline characteristics of the two groups. Detailed analysis of additional risk factors will be limited to persons with 6, 12 or 24 months of follow-up. Multivariable logistic regression models will investigate the factors associated with virologic failure at 6 months, 12 months and 24 months after CAB+RPV LA initiation. Potential explanatory variables are listed above. We will also investigate the impact of missed doses and use of oral bridging therapy by using the data collected via the CRF. Multivariate analyses will be performed when > 30 persons on CAB+RPV LA have virologic failure and analyses will be limited to persons with > 6-, 12- or 24-months follow-up. The model building strategy will follow EuroSIDA protocol and include variables significant in univariate analyses as well as *a priori* pre-specified variables of interest. Primary analysis for clinical effectiveness will include individuals on CAB+RPV LA, with VL of <50/copies/mL at regimen initiation. In addition, all the analyses will be conducted separately for individuals on CAB+RPV LA with VL of ≥50 copies/mL at regimen initiation.

Our primary analyses of virologic outcomes will censor follow-up at discontinuation of CAB+RPV LA, last visit or death, whichever occurs first, an on-treatment approach to analysis. Sensitivity analyses will use an intent to treat approach and virologic outcomes will be assessed regardless of regimen discontinuation.

We will perform additional sensitivity analysis limited to those who start CAB+RPV LA with resistance data available, to confirm no present or past evidence of viral resistance to, and no prior virological failure with agents of the NNRTI and INSTI class.

AIM 4. Monitor for resistance and next treatment response among individuals who switched off CAB+RPV LA regimen

Monitoring for resistance

Since this is a non-interventional study aiming to capture individual care in real world setting, the study will not mandate resistance testing following discontinuation of the regimen of interest. Health care providers following the local treatment guidelines decide

what laboratory and resistance tests are to be conducted. Data thus generated will be captured and analyzed by the study team.

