Descriptive analyses will compare those with and without virologic success at 12, 24, 36 and 48 months after stopping the CAB+RPV LA regimen, as well as the next regimen started and time to start the next regimen following discontinuation of the regimen. If numbers allow for further analyses, multivariable logistic regression models will investigate the factors associated with virologic success at 12, 24, 36 and 48 months after switching off CAB+RPV LA regimen. Potential explanatory variables are listed above. Multivariate analyses will be performed when > 30 persons in the relevant treatment group have virologic success and analyses will be limited to persons with > 12 months follow-up. The model building strategy will follow EuroSIDA protocol and include variables significant in univariate analyses as well as *a priori* pre-specified variables of interest.

AIM 5. Evaluate the effectiveness of routine risk minimisation measures for regimen adherence, discontinuation due to incorrect route of administration and off-label use of CAB+RPV LA regimen

The purpose of this aim is to monitor to see if label guidance is adhered to, off label usage, adherence and discontinuation due to incorrect route of administration. This analysis on effectiveness of routine risk minimisation measures will be stratified for each region in the Eurosida cohort.

Analysis of off-label users – regimen combinations other than CAB+RPV LA (b -g in objective 1)

Descriptive Analysis:

As noted in Aim 1 above, analysis will be performed on the off-label users of CAB and/or RPV LA containing regimens. They will be characterized using demographics, clinical, immunologic and virologic characteristics at baseline (i.e. at initiation of regimen) stratified by different regimens noted in groups b-g above.

Adherence and Discontinuation:

Non-adherence to the dosing schedule and discontinuation due to incorrect route of administration will be assessed as described under Aim 2.

Clinical Outcomes:

Analysis will be conducted for the off-label users of CAB and/or RPV LA containing regimens separately to assess clinical outcome similar to description under Aim 3 above.

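### The primary set is called per label on viral load alone, and Aim 5 has no off-label category for suppressed starters with prior NNRTI/INSTI failure or resistance

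*Protocol*

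**What the plan says.** The indication appears in the abstract and in section 6.1. It covers "adults who are virologically suppressed (HIV-1 RNA <50 copies/mL) on a stable antiretroviral (ART) regimen", and adds the condition "without present or past evidence of viral resistance to, and no prior virological failure with agents of the NNRTI and INSTI class".

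Section 8.3.2 limits the primary effectiveness analysis to "only those initiating the regimen per label i.e. initiating CAB+RPV LA with VL<50 copies/mL at regimen initiation". Section 8.6, Aim 3, repeats the criterion: "Primary analysis for clinical effectiveness will include individuals on CAB+RPV LA, with VL of <50/copies/mL at regimen initiation".

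Objective 5 in section 7 has two lines on who is treated outside the label. One is "Assess off-label use as described in objective 1", which points to a list of regimen combinations. The other is "Estimate proportion of treatment naive or individuals not suppressed initiating regimen". In section 8.6, Aim 5, the analysis of off-label users is headed "regimen combinations other than CAB+RPV LA (b -g in objective 1".

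Section 8.3.3 lists among the variables at initiation "History of previous virologic failure", earlier use of INSTI- or NNRTI-based regimens, and earlier drug resistance where available. Aim 3 also plans a sensitivity analysis, confined to starters with resistance data, that applies the resistance and prior-failure conditions. Section 8.8 warns that resistance results may exist for only a low proportion.

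**The concern.** The words in section 8.3.2 equate the label with one of its conditions. The protocol itself fixes this definition, and it disagrees with the protocol's own statement of the indication, so it is not a detail left open for a SAP.

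Aim 5 is where this matters most. Its stated purpose is to see whether label guidance is followed, as a measure of routine risk minimisation. The indication singles out NNRTI/INSTI resistance and failure history, yet no off-label component picks up that history. A reader of the final report could take the off-label results as complete, and could take the primary failure proportion as describing use within the label.

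**Working it through.** **1. Conditions side by side.**

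| Condition in section 6.1 | Required for the primary set (8.3.2, 8.6 Aim 3)? | Counted as off-label (objective 5, Aim 5)? |
|---|---|---|
| CAB+RPV LA as the complete regimen | Yes | Yes, through the other regimen groups |
| HIV-1 RNA <50 copies/mL | Yes | Yes, unsuppressed starters in objective 5 |
| On a stable ART regimen | Not stated | In part: treatment-naive starters only |
| No past or present NNRTI/INSTI resistance | No | No |
| No prior failure on NNRTI/INSTI | No | No |

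**2. One person traced through the rules.** Take a CAB+RPV LA starter with viral load <50 and a documented earlier failure on an NNRTI. Section 6.1 places this person outside the indication. Section 8.3.2 admits the person to the set it calls per label. Objective 5 does not count the person: the regimen is the approved one, and the person is neither naive nor unsuppressed. Aim 5's off-label analysis does not reach the person either. The omission has no effect only if nobody with such a history starts the regimen.

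**3. Are the data planned?** Largely. Section 8.3.3 lists the histories, section 8.2 records start and stop dates of each ARV, and Table 3 has stop codes for virological failure (1.1) and resistance (1.5). The additional form collects documented resistance history at initiation, and the Annex 1 CRF asks for the latest pre-initiation resistance report.

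**4. Size, on assumptions only.** The protocol gives no prevalence *f* of such a history among suppressed starters and no failure risk for them.

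- People affected: N × *f*. With N = 500, 500 × 0.05 = 25 and 500 × 0.15 = 75.
- Primary estimate: observed risk = (1 − *f*) × p0 + *f* × p1. With p0 = 1% and p1 = 4%, *f* = 5% gives 0.95 × 1% + 0.05 × 4% = 1.15%, and *f* = 15% gives 0.85 × 1% + 0.15 × 4% = 1.45%. The shift is 0.15 to 0.45 points.
- For scale, the exact Clopper-Pearson 95% interval for 5 failures in 500 is 0.0033 to 0.0232, a width of 0.0199. Table 4 prints an upper limit of 0.23 in that row, which does not reproduce, so the recomputed value is used.
- Wider range with p0 = 2% (a Table 4 scenario) and *f* = 5%, 10%, 20%: a doubled risk gives 2.1%, 2.2%, 2.4%; a fivefold risk gives 2.4%, 2.8%, 3.6%. The recomputed exact interval at N = 500, P = 0.02 is 0.0096 to 0.0365. Only the most extreme combination, a shift of 3.6% − 2% = 1.6 points, comes near its upper limit.

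**The case against.** Several parts of the defence stand.

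- *Effectiveness is partly covered.* The Aim 3 sensitivity analysis applies the resistance and prior-failure conditions, and testing is not routine in many clinics. A primary set defined by viral load with a restricted sensitivity analysis is defensible for routine-care data. What remains is the label attached to the set, and the restriction to people with resistance data. Prior failure can be judged from treatment and viral load history without a resistance test.
- *These people are not invisible.* Aim 1 describes baseline clinical characteristics by regimen group, and section 8.3.3 includes the relevant histories. They can appear in those tables and as model covariates. Appearing in a baseline table is still not the same as being classified as off-label.
- *The data are imperfect.* Section 8.3.3 lists virologic failure without class, so class-specific failure must be reconstructed. The CRF uploads only the latest pre-initiation resistance report, so past resistance may be incomplete. This argues for an unknown category. It does not justify treating known cases as on-label.

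A reader might infer that the off-label proportion would be 5 to 15 points too low. The documents do not support that figure. The protocol lists separate components and defines no overall off-label proportion, and the prevalence is assumed. Even for an invented composite the denominator matters: with 5% of starters already flagged, the total becomes 0.05 + 0.95 × *f*, so *f* = 5% adds 0.95 × 5% = 4.75 points, not 5.

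**Conclusion.** The point holds as a mismatch between the protocol's indication and its stated rules. Followed exactly, the rules never classify as off-label a suppressed CAB+RPV LA starter with known NNRTI/INSTI resistance or failure. The weight lies on objective 5 and Aim 5. The number affected cannot be derived from the documents, and the 25 to 75 of 500 above rests wholly on an assumed 5% to 15%.

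A reader might also infer that the primary failure estimate is materially biased. That is not shown. Under the assumed 1% and 4% risks the shift of 0.15 to 0.45 points lies well inside an interval about 2 points wide. A shift comparable with the sampling error needs both a 20% prevalence and a fivefold risk, and nothing in the protocol supports either. The effect is probably small and partly covered by the planned sensitivity analysis. Confidence is high for the mismatch in definitions and low for any figure of impact.

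**What to change.** 1. In objective 5 and Aim 5, add an off-label component: *CAB+RPV LA starters with documented NNRTI/INSTI resistance or prior virologic failure on either class*. Derive it from the planned ARV, viral load and resistance history. Show *unknown* as its own row, and report each off-label reason separately with its denominator, since reasons can overlap.
2. In sections 8.3.2 and 8.6, describe the primary set as *VL <50 copies/mL at initiation* and drop the claim that it is per label.
3. Beside the primary result, report a sensitivity analysis that excludes starters known not to meet any condition of the indication in section 6.1, including the stable regimen, and that is not restricted to people with resistance data. The protocol does not define stable, so the derived variable needs a stated working definition.

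The third analysis should stay a sensitivity analysis. Excluding only known cases depends on who was tested, and section 8.8 says testing may be targeted, so untested people with the same history would remain.

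The cost is wording, some derivation work and an unknown-history row, with history incomplete for some people. No new data collection is required.

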7. RESEARCH QUESTIONS AND OBJECTIVE(S)

Following the initiation of any ARV regimen containing CAB and/or RPV LA among PLWH, the study will aim to assess usage patterns, durability, discontinuation, and virologic outcomes.

The specific objectives are to:

- 1. Describe CAB and/or RPV LA containing regimens usage patterns
 - Descriptive analysis of study population by baseline demographic and clinical characteristics
 - Monitor for use of oral lead-in
 - The potential regimen combinations are listed below (Note that CAB+RPV LA is the only approved regimen)
 - a. CAB+RPV LA regimen only
 - b. CAB LA monotherapy
 - c. CAB LA use in combination with ARVs other than RPV LA
 - d. RPV LA monotherapy
 - e. RPV LA use in combination with ARVs other than CAB LA
 - f. CAB LA+RPV LA+other ARVs
 - g. Combined group b-f
- 2. Assess adherence, durability and discontinuation for persons starting CAB+RPV LA regimen;
 - Proportion of individuals discontinuing the regimens of interest will be assessed.
 - Reasons for discontinuation will be assessed.
 - Non-adherence to the dosing schedule will be assessed by:
 - a. Estimating the number of individuals that missed one or more consecutive injections without taking daily oral bridging therapy or any other oral ARV regimen while not on CAB+RPV LA containing regimens and mean and median number of injections missed during a 12-month period
 - b. Estimating the number of individuals who received the injections seven or more days later than their scheduled injection visit and median duration of delayed injections
 - c. Estimating the number of individuals who missed one or more consecutive injections without taking daily oral bridging therapy or those who received the injections seven or more days later than their scheduled injection visit (Combined group a OR b) and describe patient characteristics for the individuals that are nonadherent.
 - Number of individuals with incorrect route of administration will be described.

- 3. Assess the clinical effectiveness (i.e. proportion of individuals experiencing virologic failure) among PLWH who initiate CAB+RPV LA regimen
 - a. Estimate the proportion of individuals with virologic failure, during the first 6 months after initiation of CAB+RPV LA
 - b. Estimate the proportion of individuals with virologic failure, at 6, 12 and 24 months after initiation of CAB+RPV LA
 - c. Stratified analyses for 3a and 3b will be conducted for VL at regimen initiation (<50 copies/mL and ≥50 copies/mL).

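### The confirmed virologic failure rule suits people who start suppressed, but it is also applied during the first 6 months to CAB+RPV LA starters with VL ≥50, where a falling VL from ≥200 can count as failure

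*Protocol*

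**What the plan says.** Protocol section 8.3.2 (Clinical effectiveness) gives CVF two limbs. The first is "Two consecutive HIV RNA VL levels ≥200 copies/mL". The second is "One HIV RNA VL level ≥200 copies/mL and regimen discontinuation within 4 months of VL ≥200 copies/mL". Neither limb requires an earlier suppressed value or a minimum time on the regimen, and the protocol does not say whether the baseline VL may be one of the values. The measure is the "Proportion of individuals with confirmed virologic failure (CVF) during the first 6 months, and at 6, 12 and 24 months".

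The primary effectiveness analysis is restricted to those "initiating CAB+RPV LA with VL<50 copies/mL at regimen initiation". The same measure is then carried to other starters:

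- Objective 3a (section 7): "Estimate the proportion of individuals with virologic failure, during the first 6 months after initiation of CAB+RPV LA".
- Objective 3c (section 7): "Stratified analyses for 3a and 3b will be conducted for VL at regimen initiation (<50 copies/mL and ≥50 copies/mL").
- Section 8.6, Aim 3: "all the analyses will be conducted separately for individuals on CAB+RPV LA with VL of ≥50 copies/mL at regimen initiation". No separate failure definition is given for this group.

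The protocol expects such starters. Objective 5 includes the item "Estimate proportion of treatment naive or individuals not suppressed initiating regimen", and section 8.3.3 lists starting VL categories up to ≥100,000 copies/mL.

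**The concern.** For someone who starts below 50, any VL ≥200 is a rise, so both limbs describe loss of control. For someone who starts at ≥200, the failure threshold lies inside the entry state, and the rule cannot tell a VL that has not yet fallen from one that has come back.

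The first limb is met by two early tests on a falling curve. The second is met by one such test and a stop within 4 months for any reason. Table 3 lists stopping reasons that say nothing about virologic response, such as injection site reaction and pregnancy. If the baseline value counts, everyone starting at ≥200 who stops within 4 months of that value is a CVF.

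At stake is the 3a result in the ≥50 stratum. Two sites with identical responses could report different failure proportions because one tests earlier or more often, or treats people with higher starting VL. A reader who sets the two strata of objective 3c side by side would compare a rebound proportion with a mixture of non-response and normal decline.

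**Working it through.** The protocol states no figure to reproduce. The check sets the rule against the people it is applied to, then asks when a responder would meet it.

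**Step 1: who can be misclassified.** Primary population (<50 at start): nobody, since a value ≥200 is a rise. Starters at 50–199: nobody while VL falls. Starters at ≥200: possible.

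**Step 2: the fall needed.** log10(10,000/200) = 1.70 and log10(100,000/200) = 2.70. For 500,000, which lies in the top category, log10(500,000/200) = 3.40.

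**Step 3: how long a responder stays at ≥200.** The decay rates are assumptions, not from the documents: 1 log10 per d1 days for the first 2 log10, then 1 log10 per d2 days, with (d1, d2) = (7, 30), (10, 45) or (14, 60). For a required fall L, days at ≥200 = min(L, 2) × d1 + max(0, L − 2) × d2. Example, 100,000 at the fastest decay: 2 × 7 + 0.699 × 30 = 35.0 days.

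| Starting VL | Fast | Middle | Slow |
|---|---|---|---|
| 1,000 | 4.9 | 7.0 | 9.8 |
| 10,000 | 11.9 | 17.0 | 23.8 |
| 100,000 | 35.0 | 51.5 | 69.9 |
| 500,000 | 55.9 | 82.9 | 111.9 |

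**Step 4: does a responder meet the first limb?** Tests are assumed every 14, 28 or 56 days from the first injection.

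- 1,000: never.
- 10,000: only with 14-day testing, baseline counted, and middle or slow decay.
- 100,000, baseline counted: always with 14- or 28-day testing; with 56-day testing only at slow decay.
- 100,000, baseline not counted: always with 14-day testing; with 28-day testing only at slow decay; never with 56-day testing.
- 500,000, baseline counted: always with 14- or 28-day testing; with 56-day testing at middle and slow decay.
- 500,000, baseline not counted: always with 14-day testing; with 28-day testing at middle and slow decay (at fast decay VL passes below 200 at 55.9 days, just before the day-56 test); never with 56-day testing.

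The result therefore turns on starting VL, test timing and a baseline convention that the protocol does not state.

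**Step 5: the later time points.** Section 8.6 (Aim 3) assesses 6 months within ±6 weeks. The window opens at 182.6 − 42 = 140.6 days, or about 4.6 months. The slowest trajectory above is below 200 by 111.9 days, before the window opens. The 6-, 12- and 24-month assessments are thus largely clear of the problem. The qualification is needed because the fallback for people with no VL in the window also mentions a first measurement within the first six months, which could bring an early value back in.

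**The case against.** The strongest reply is that this is a side analysis with safeguards. Primary effectiveness is confined to starters below 50. Section 8.3.2 also reports VL <50 and VL <200 at 6, 12 and 24 months, and section 8.6 repeats all analyses in the ≥50 group, so a reader would have suppression figures beside CVF. Analysis follow-up begins at the first injection (section 8.3.1). Where the oral lead-in of at least 28 days described in section 6.1 is used, part of the decline comes before it. Testing follows routine care and may be too sparse to give two early values.

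All of this stands, and it limits the scope. It does not remove the defect: the first-6-months CVF proportion in the ≥50 stratum is itself a stated output, and stratifying leaves the rule unchanged inside the affected stratum. Nor is this detail left to an analysis plan, because the protocol states both the rule and the group it applies to.

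A second objection is also sound. Simply requiring earlier suppression, or a VL at or after month 6, would lose a real failure: someone who never suppresses and stops at month 3 with VL ≥200 would meet neither condition, and on-treatment follow-up is censored at discontinuation. The present second limb catches that person, so any replacement must too.

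**Conclusion.** The point holds for one result: the first-6-months CVF proportion (objective 3a) among CAB+RPV LA starters with VL ≥50. Within that stratum it concerns those starting at ≥200. A responder there can be counted as a failure, but will not always be.

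Four stronger readings are tempting but not supported:

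- That starting VL becomes a built-in risk factor in the failure models. Those models are for failure at 6, 12 and 24 months, need more than 30 failures, and are run separately in the ≥50 group.
- That the off-label regimens are equally affected. Objective 3d and the Aim 5 models use 6, 12 and 24 months. A first-6-months count there follows only from the general statement that Aim 5 resembles Aim 3.
- That objective 5 is biased. Its item on unsuppressed people is the proportion who initiate, which does not use CVF.
- That the inflation can be quantified. Assuming 10% true non-response and 20–60% of responders with two early values ≥200 gives 0.10 + 0.90 × 0.2 = 28% to 0.10 + 0.90 × 0.6 = 64%. The documents support neither assumption: they give neither the number starting at ≥200 nor the testing frequency. The range shows only how sensitive the proportion is.

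The size therefore cannot be computed. The day counts under working rest on assumed decay rates and test intervals. The statement that the rule can misclassify a responder rests on the protocol text alone.

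**What to change.** In section 8.3.2, keep the present rule for starters with VL <50. For CAB+RPV LA starters with VL ≥50, and for off-label regimens if a first-6-months count is made there, state that the baseline VL is not one of the qualifying values and count as failure:

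1. Rebound: the present rule, applied only to VLs after the first on-treatment VL <50.
2. Non-suppression: VL ≥200 at the 6-month window or later, confirmed or followed by discontinuation within 4 months, with no earlier suppression.
3. Early discontinuation without suppression: discontinuation before month 6 with the last on-treatment VL ≥200 and no earlier suppression. Show this as a separate line by reason for stopping, so that early non-responders are kept and can be told apart from people who stopped for other reasons.

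For objective 3a in this stratum, report the proportion reaching VL <50 by 6 months beside these categories.

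The cost is one paragraph and the matching program code, using data already collected. The primary endpoint does not change. The two strata would no longer share one failure definition, which needs a footnote. The footnote should also say that a starter at 50–199 whose VL rises to ≥200 before month 6 without reaching <50 would be counted through the second or third category and not at the time of the rise.
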